### Mobile phone battery analysis

Data will be baseline adjusted and analysed by ANOVA (treatment (placebo and active) by day (7, 14, 21 and 28) by time (am and pm).

### State Trait Anxiety Inventory (STAI)

Trait anxiety scores, collected during the screening/training visit will be compared between the treatment conditions to ensure that no differences exist between groups on this stable anxiety factor.

State anxiety scores, collected prior to pre-dose cognitive tasks on day 1 and on day 29, will be converted into a change score (day 29 score minus day 1) and compared between treatments via ANOVA.

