**Ethics code: 8970**

## **STUDY DESIGN AND PLAN**

The study will follow a randomised, double-blind, placebo-controlled, parallel groups design.

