## **STUDY PROCEDURES**

Testing will take place in a suite of testing facilities with participants visually isolated from each other. Participants will attend the laboratory on 3 separate occasions, an introductory visit between 1 and 14 days before the first day of treatment, and two testing days (Day 1 and Day 29):

[figure not shown]
The Introductory visit to the laboratory will comprise: briefing on requirements of the study, obtaining of informed consent, health screening, completion of the Caffeine Consumption Questionnaire (CCQ) and State-Trait Anxiety Inventory (STAI) trait subscale, training on the cognitive and mood measures and collection of demographic data.

For the two ensuing laboratory-based testing sessions (Day 1, Day 29) participants will attend the laboratory before 8.00 am having consumed a standardised breakfast of cereal and/ or toast at home no later than an hour before arrival. They must have refrained from alcohol for 24 hours and caffeine for 18 hours. On arrival on each day participants will complete the State-Trait Anxiety Inventory (STAI) state subscale and the computerised cognitive assessment (as per Figure 1) followed by measurements of blood-pressure and heart rate. Immediately following this they will consume their treatment for that day. Two further cognitive assessments (plus BP and HR), identical to the pre-dose assessment will commence at 120- (~11:00 am) and 240 (~02:00 pm) minutes post-dose; the latter in order to take advantage of natural declines in performance during the day. Participants will be given a standardised lunch at approximately 12:10 pm. This lunch will comprise a white bread cheese sandwich, packet of ready salted crisps and custard pot.

[figure not shown]
Cognimapp mobile phone assessments will take also place outside of the laboratory before the treatment period begins (Day -6 to -1) and at intervals of 7 (+/- 1 day) days (e.g. Day 7, 14, 21, 28) with the final assessment taking place the day before the final laboratory visit. Assessments will take place in the morning (pre-dose) and evening on each day.

Participants will be prompted by text messaging. Additionally, on Day 24, participants will complete the learning phase of the location-learning task. On day 28 the Cognimapp assessment will include completion of the retrieval phase of the location-learning task.

[figure not shown]

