#### *Treatment schedule across the study*

Participants will be provided with at least 30 days supply of the study's investigational products (sage or placebo) for consumption daily between testing visits Day1 and Day 29 and will undergo the cognitive/mood assessment on the first day (Day 1) and the last day (Day 29) of the active treatment period. The allocation to treatments will be undertaken via a randomly generated treatment schedule.

Details of the mood assessments, COMPASS battery, CDB battery and mobile phone battery are presented in Appendices I, II, III and IV.

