#### 3. Acute, and superimposed effects

- i) To ascertain if any acute effects on day 1 have increased or attenuated over the 29 day treatment period, data from day 1 and day 29 will be baseline adjusted with respect to the respective day's baseline assessment and entered into a three way (day x assessment x treatment) ANOVA.
- ii) To ascertain if there are differential chronic effects pre and post-dose on day 29, pre and post dose data from day 29 will be baseline adjusted with respect to the pre-dose baseline on day 1 and subjected to a two way ANOVA (treatment x assessment).

The proposed a priori and post-hoc comparisons between treatment means to be utilised will be specified in the Statistical Analysis Plan

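### Comparing trait anxiety between randomised arms cannot ensure balance; describe it by arm and use it, with day 1 state anxiety, as a prespecified covariate (minor, mainly precision)

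*Protocol*

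**What the plan says.** The trial has a "randomised, double-blind, placebo-controlled, parallel groups design" (Protocol, Study Design and Plan), and "The allocation to treatments will be undertaken via a randomly generated treatment schedule" (Protocol, Treatment schedule across the study). The trait subscale is completed at the introductory visit, 1 to 14 days before treatment starts (Protocol, Study Procedures).

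The section State Trait Anxiety Inventory (STAI) then makes two statements:

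- Trait scores "will be compared between the treatment conditions to ensure that no differences exist between groups on this stable anxiety factor".
- For the state subscale, which participants fill in before that day's treatment at each of the two laboratory testing visits, the plan is that the pair of values "will be converted into a change score (day 29 score minus day 1) and compared between treatments via ANOVA".

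The protocol names no test or threshold for the trait comparison and no action to follow from it. It gives the trait score no other use, and it names no covariate for the state-anxiety ANOVA.

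**The concern.** The stated method cannot reach the stated aim. Under random allocation, a difference in a pre-treatment score arises by chance. A formal test of it therefore tests a hypothesis already known to be true, and flags about one trial in twenty at the 5% level. A non-significant result does not show that the arms are alike, least of all in a small trial.

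The comparison thus offers reassurance that it cannot support, while a baseline score collected from every participant goes unused in the analysis where it could help. At stake is some precision in the state-anxiety contrast, and some protection against chance imbalance, both available from data already being gathered.

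**Working it through.** **Inputs.** The protocol states no sample size, significance level, SD or correlation, so there is no figure to reproduce. Everything below is an illustration under these assumptions: 1:1 allocation, two-sided 5%, and equal state SDs on both days. r1 and r29 are the trait-state correlations on day 1 and day 29, and rho is the correlation between the two state scores.

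**1. What the comparison can detect.** The largest observed standardised difference that is still non-significant is about 1.96 × √(2/n), with n per arm:

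| n per arm | Largest non-significant imbalance (SD) |
|---|---|
| 20 | 0.62 |
| 40 | 1.96 × 0.224 = 0.44 |
| 60 | 0.36 |
| 80 | 0.31 |

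An observed imbalance of 0.4 SD would pass unflagged at 20 or 40 per arm. In 20,000 simulated randomised trials with 40 per arm, the test flagged 5.4%, close to the nominal 5% expected when only chance operates.

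**2. What a trait imbalance does to the state-anxiety result.** For a trait imbalance of d SD, the expected shift in the between-arm difference, in state SDs, is:

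- day 29 state alone: r29 × d
- change score, as planned: (r29 − r1) × d
- ANCOVA on day 1 state only: (r29 − rho × r1) × d
- ANCOVA on day 1 state and trait: 0 for the linear part

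With d = 0.4:

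| r1, r29 | Day 29 alone | Change score | ANCOVA, day 1 only (rho 0.7 to 0.5) |
|---|---|---|---|
| 0.5, 0.5 | 0.20 | 0 | 0.06 to 0.10 |
| 0.6, 0.6 | 0.24 | 0 | 0.07 to 0.12 |
| 0.5, 0.4 | 0.16 | −0.04 | 0.02 to 0.06 |
| 0.6, 0.5 | 0.20 | −0.04 | 0.03 to 0.08 |
| 0.4, 0.6 | 0.24 | +0.08 | 0.13 to 0.16 |

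The same simulation (r1 = r29 = 0.5, rho = 0.6) gave a slope on trait imbalance of 0.50 for day 29 state and −0.01 for the change score, against a true value of 0. The subtraction removes the trait contribution that is common to both days.

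**3. What a day 1 state imbalance does.** The change score over-corrects by (rho − 1) × d. For d = 0.4 this is −0.20 SD at rho = 0.5 and −0.12 SD at rho = 0.7.

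**4. Precision.** Residual variance, in units of the state variance, with r1 = r29 = r = 0.5:

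- change score: 2(1 − rho)
- ANCOVA on day 1 state: 1 − rho²
- ANCOVA on both: 1 − (rho² + r² − 2 × rho × r²)/(1 − r²)

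At rho = 0.6 the last is 1 − (0.36 + 0.25 − 0.30)/0.75 = 0.59.

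| rho | Change score | Day 1 state | Day 1 state and trait | Reduction from change score |
|---|---|---|---|---|
| 0.5 | 1.00 | 0.75 | 0.67 | 33% |
| 0.6 | 0.80 | 0.64 | 0.59 | 27% |
| 0.7 | 0.60 | 0.51 | 0.48 | 20% |

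Most of the gain comes from day 1 state. Adding trait alone to the change-score ANOVA would gain almost nothing here, because with r1 = r29 the trait score is uncorrelated with change.

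**The case against.** A reader might infer that a chance imbalance in trait anxiety passes straight into the state-anxiety result. The protocol does not support that. The sentence after the trait comparison analyses a within-person change from a pre-treatment score, and the protocol itself treats trait anxiety as a stable factor. A contribution equal on both days cancels, so only a trait effect on change could carry over. Nothing in the document indicates that there is one or how large it might be.

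Three further objections have weight.

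- Chance imbalance under randomisation is not bias. The unadjusted ANOVA's standard error already allows for it. This stands, and it is why the point concerns precision and not validity.
- The protocol speaks only of a comparison. It sets no 5% threshold and does not say that non-significance will be taken as balance. This also stands: the 0.44 SD figure illustrates a conventional test and is not a rule in the plan.
- Covariates are commonly left to the SAP, which is not at hand. That is true, and the lack of a covariate is not in itself the finding. But the deferral in the section on acute and superimposed effects, "The proposed a priori and post-hoc comparisons between treatment means to be utilised will be specified in the Statistical Analysis Plan", does not reach the trait comparison. The protocol states that comparison and its aim outright, and a covariate added in the SAP would not correct the sentence.

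**Conclusion.** The point holds in limited form. Comparing randomised arms on trait anxiety cannot ensure that they do not differ, and the protocol gives the score no other role. The change score already removes any trait contribution that is the same on both days. What remains unadjusted is a trait effect on change (−0.04 to +0.08 SD for a 0.4 SD imbalance when the two trait-state correlations differ by 0.1 to 0.2, and none when they are equal) and regression to the mean from a day 1 state imbalance (−0.12 to −0.20 SD for a 0.4 SD imbalance). The second is a day 1 state problem and not a trait problem.

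All these sizes rest on assumed sample sizes, correlations and imbalances. Severity is minor: the comparison triggers no decision, and nothing in the protocol makes state anxiety a primary outcome.

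**What to change.** In the STAI section of the protocol:

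1. Delete the between-group comparison of trait scores and its stated aim of ensuring no difference. Report trait anxiety descriptively by arm, without a test.
2. Replace the change-score ANOVA with an ANCOVA of day 29 state anxiety that includes day 1 state and screening trait scores as covariates. Prespecify both, whatever imbalance is observed. Using the change score as the outcome with the same two covariates gives the same treatment estimate.
3. Keep both covariates together. Trait added to the change-score ANOVA may gain almost nothing. Day 1 state without trait leaves more of a trait imbalance in the result than the change score does (0.06 to 0.12 SD against 0, for d = 0.4 with equal trait-state correlations of 0.5 to 0.6).

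The cost is a change of wording and two degrees of freedom. Both scores are already collected, so no new data are needed.

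### State anxiety is tied to an unadjusted change-score ANOVA, which is valid but usually less precise than ANCOVA on the Day 1 score already collected

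*Protocol*

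**What the plan says.** Under State Trait Anxiety Inventory (STAI), the protocol takes "State anxiety scores, collected prior to pre-dose cognitive tasks on day 1 and on day 29" and states that they "will be converted into a change score (day 29 score minus day 1) and compared between treatments via ANOVA". No covariate is named.

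Three other places bear on the point:

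- Study Design and Plan: "The study will follow a randomised, double-blind, placebo-controlled, parallel groups design". Treatment schedule across the study names two arms, "investigational products (sage or placebo)".
- Study Procedures, on timing: "On arrival on each day participants will complete the State-Trait Anxiety Inventory (STAI) state subscale". The cognitive assessment and the blood pressure and heart rate readings come next, and then "Immediately following this they will consume their treatment for that day".
- Acute, and superimposed effects, on what is left for later: "The proposed a priori and post-hoc comparisons between treatment means to be utilised will be specified in the Statistical Analysis Plan". This defers the choice of contrasts. It does not defer the state-anxiety model, which the STAI section sets.

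**The concern.** A change score subtracts the whole of the Day 1 value from the Day 29 value. That is the most precise use of the baseline only if a participant who starts one point higher is expected to finish one point higher. If the true slope is below 1, subtraction over-corrects and adds Day 1 noise to the comparison. If it is above 1, subtraction under-corrects.

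State anxiety is a momentary measure and the two readings are four weeks apart. The same section of the protocol contrasts it with trait anxiety, which it treats as stable. A slope below 1 is therefore a reasonable expectation, though the document gives no figure for it.

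Precision is at stake, not validity: a wider confidence interval and lower power on state anxiety, with nothing gained in return.

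**Working it through.** **Inputs.** From the protocol: randomised parallel groups, two arms, and a Day 1 state score taken before dosing. Randomisation gives the Day 1 score equal expectation in both arms, so adjusting for it introduces no bias. The protocol shows no sample size, SD, correlation or effect size, so there is no stated figure to reproduce. Assumed here:

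- correlation rho between Day 1 and Day 29 of 0.3 to 0.9;
- SD ratio k = SD29/SD1 of 0.8, 1 or 1.25;
- n = 30 per arm, with other sizes where stated;
- an effect of 0.5 Day 1 SD for power.

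**Variances.** Set SD1 = 1, so the true slope is b = rho × k. Per participant, within arm:

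- change score: k² + 1 − 2·rho·k
- ANCOVA, large sample: k²(1 − rho²)
- difference: 1 − 2·rho·k + rho²k² = (1 − b)²

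The difference is never negative and is zero only when b = 1. The change-score contrast also shifts with any chance Day 1 imbalance, by −(1 − b) times that imbalance. This shift is the same loss seen another way and should not be counted twice.

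**Equal SDs (k = 1).** The ratio of ANCOVA to change-score variance is (1 − rho²)/(2(1 − rho)) = (1 + rho)/2. At rho = 0.5, for example, it is 0.75/1.00 = 0.75.

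**Cost of estimating the slope.** This multiplies the ANCOVA variance by 1 + 1/(2n − 4). At n = 30 that is 1 + 1/56 = 1.018, and at n = 50 it is 1 + 1/96 = 1.010.

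Power below is two-sided at 5% from the noncentral t, with 2n − 2 degrees of freedom for the change score and 2n − 3 for ANCOVA.

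| k | rho | Variance ratio, large sample | Variance ratio, n = 30 | Power, change score | Power, ANCOVA |
|---|---|---|---|---|---|
| 1 | 0.3 | 0.65 | 0.66 | 36% | 51% |
| 1 | 0.5 | 0.75 | 0.76 | 48% | 59% |
| 1 | 0.7 | 0.85 | 0.87 | 69% | 75% |
| 1 | 0.9 | 0.95 | 0.97 | 99% | 99% |
| 0.8 | 0.3 | 0.50 | 0.51 | 42% | 70% |
| 0.8 | 0.7 | 0.63 | 0.64 | 75% | 91% |
| 1.25 | 0.3 | 0.78 | 0.80 | 29% | 35% |
| 1.25 | 0.7 | 0.98 | 1.00 | 56% | 56% |
| 1.25 | 0.8 | 1.00 | 1.02 | 72% | 71% |

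**Where the gain disappears.** With equal SDs and 30 per arm, break-even is (1 + rho)/2 × 1.018 = 1, so rho = 0.965. With k = 1.25 and 30 per arm, ANCOVA gives no gain for rho between about 0.71 and 0.87. The worst point is rho = 0.8, where b = 0.8 × 1.25 = 1 and ANCOVA loses 1.8%.

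**Simulation.** In 40,000 trials per setting at 30 per arm with k = 1, the variance ratios were 0.662, 0.766, 0.859 and 0.966 at rho 0.3, 0.5, 0.7 and 0.9, in line with the formula. Under no treatment effect both estimators averaged about zero in every setting.

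**The case against.** The strongest reply is that nothing here is wrong. A change-score ANOVA is a standard and correct analysis of a randomised two-arm trial, so preferring ANCOVA comes close to a matter of taste. That stands as far as validity goes. It does not justify giving up precision when the protocol states no reason to prefer the change score.

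Second, the loss cannot be shown from the document. Correlation, SDs, sample size and effect size are all assumed, and nothing makes equal SDs certain. With an SD ratio of 1.25 the power gain is 6 percentage points at rho 0.3 and nothing at 0.7. This also stands: the percentages show what may be lost under stated assumptions and do not estimate this trial's loss.

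Third, the 2% worst case belongs to 30 per arm. In a smaller trial it is larger: 1/36 = 2.8% at 20 per arm and 1/26 = 3.8% at 15. That is correct, and still small beside the possible gain.

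Fourth, the SAP is not at hand and could add the covariate. Adding the Day 1 score to the change-score model gives the same treatment estimate as ANCOVA on Day 29, so the change score itself is no obstacle. But the protocol specifies a plain ANOVA for this outcome and defers only comparisons between treatment means. As written, the model is stated and is not a gap left open.

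**Conclusion.** The point holds, as an efficiency improvement that should be made. The planned state-anxiety analysis is valid, and no conclusion is put at risk. In large samples it is less precise than ANCOVA unless the true slope is 1, and the excess variance is proportional to (1 − slope)².

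The trade is lopsided. At 30 per arm with equal SDs, ANCOVA saves about 3% to 34% of the variance for correlations from 0.9 down to 0.3, and the saving is larger if the Day 29 SD is the smaller one. Against that, the most it can lose is about 2%, when the true slope is close to 1.

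Confidence in the direction is high. Confidence in the size is limited, because the protocol supplies none of the quantities that determine it. The protocol does not name the outcome as primary, which keeps the matter modest.

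**What to change.** Replace the state-anxiety sentence with one to this effect: Day 29 state anxiety will be analysed by ANCOVA with treatment as factor and the Day 1 pre-dose state-anxiety score as a prespecified covariate. The mean change can still be reported descriptively.

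The cost is wording only. No new data, visits or participants are needed. The statistical price is one degree of freedom and, at worst, about 2% in variance at 30 per arm. The change should be made before unblinding, because switching the estimator afterwards would look driven by the data.
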